Study drug treatment extension beyond these 30 days will be guided by a number of risk factors for relapse of the presenting TTP episode and must be accompanied by an optimization of the immunosuppressive treatment. The risk factors will include the ADAMTS13 activity profile (measured weekly), as well as other signs and symptoms of continued underlying disease activity, such as presence of inhibitors if measured as routine practice by the site. Continued study drug treatment should be given for additional 7-day periods with a maximum of 28 days for subjects whose ADAMTS13 activity profile remains below 10% based on weekly measurements and for subjects with other clinical signs of underlying disease. In parallel, optimization of the immunosuppressive treatment should be considered starting at the Week 3 visit of the 30-day post-daily PE period and includes reversal of corticosteroid tapering through increase or re-initiation of corticosteroid treatment, or start/continuation of other immunosuppressive treatment such as rituximab (to be used as per standard site practice). Study drug treatment extension should be stopped when ADAMTS13 activity shows a sustained upward trend of >10% and at the latest on Day 28 of the study drug treatment extension.

Recurrence of TTP episode

- Exacerbation is defined as recurrent thrombocytopenia after initial recovery of platelet count (platelet count $\geq 150 \times 10^9/L$ with subsequent stop of daily PE within 5 days), requiring re-initiation of daily PE, occurring during the first 30-days post-daily PE period.
- Relapse is defined as recurrent thrombocytopenia after initial recovery of platelet count requiring re-initiation of daily PE, occurring after the 30-days post-daily PE period.

Based on the mechanism of action and the available efficacy and safety results from study ALX-0681-2.1/10 (Phase II TITAN trial) it is considered desirable from both a treatment and exposure perspective (to maximize the number of subjects exposed to caplacizumab), to allow for crossover to open-label caplacizumab for subjects who experience a recurrence of the TTP episode.

Exacerbation

In case of a first exacerbation of the presenting TTP episode, subjects will receive open label caplacizumab together with daily PE irrespective of what the initial treatment allocation was.

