4.3.5 Randomized versus actual treatment

Analyses will be handled differently before and after switch to open-label caplacizumab after recurrence, as specified below.

Before switch to open-label caplacizumab the treatment group as assigned by the randomization will be used (i.e., as-randomized analysis) for efficacy. For safety, PK, PD, disease-related markers and immunogenicity analyses the treatment that was actually used by the subject will be applied (i.e., as-treated analysis).

Differences between as-treated and as-randomized will be flagged in the listing on subject allocation.

After switch to open-label caplacizumab an all-treated analysis will be conducted in a separate pooled open-label caplacizumab treatment group, unless specified otherwise. For some specific analyses, e.g. for immunogenicity analyses; see Section 9.1, this pooling is not done. As a consequence, if open label period is represented according to the randomized treatment, the actual treatment (Caplacizumab) can differ from represented treatment group (Placebo or Caplacizumab).

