4.3.6 Presentation of treatment groups

The following treatment group labels will be used in the tables, listings and figures, unless specified otherwise:

- Caplacizumab
- Placebo
- Open-label (OL) Caplacizumab

Treatment groups Caplacizumab and Placebo refer to the initial treatment group prior to a potential switch to open-label caplacizumab, and only data up to the switch are used in the analyses of these treatment groups. The OL Caplacizumab treatment group will only be used for analyses after the switch to open-label caplacizumab.

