4.4 Analysis Periods and Visit Windows

4.4.1 Analysis periods

The following analysis phases are defined for this study: Screening, Treatment, Follow-up. Within these analysis phases, the following analysis periods and subperiods will be considered:

Table 1: Analysis periods

Period	Subperiod	Start period	End period
(Screening)		Date of signing the ICF, with 00:00 added as timepart	First DB treatment administration datetime – 1 min
Double-Blind (DB) Treatment	Daily PE	First administration datetime of DB treatment	Start of DB post-daily PE subperiod – 1 min
	Post-daily PE	Date of switch to post-daily PE + 1 day with 00:00 added as timepart	Min(Week 5 visit date if no treatment extension or last visit date of treatment extension period with 23:59 added as timepart, early termination visit date with 23:59 added as timepart, first administration datetime of OL treatment – 1 min)
	Daily PE	First administration datetime of OL treatment	Start of OL post-daily PE subperiod – 1 min

CONFIDENTIAL

Open-label (OL) Treatment	Post-daily PE	Date of switch to post-daily PE + 1 day with 00:00 added as timepart	Min(Week 5 visit date if no treatment extension or last visit date of treatment extension period, early termination visit date) with 23:59 added as timepart
(Follow-up)		End of treatment period + 1 min	Trial termination date, with 23:59 added as timepart

Note that the last analysis period in case of early termination will always be ended by the trial termination date.

The 'overall treatment period' corresponds with the treatment analysis phase and covers both the DB treatment analysis period and the OL treatment analysis period. Note that only subjects who experience a relapse or exacerbation will have an OL treatment analysis period. For these subjects, the overall treatment period starts at start of DB treatment period and ends at end of OL treatment period. For subjects with no switch to open-label caplacizumab, the overall treatment period starts at start of DB treatment period and ends at end of DB treatment period.

The 'overall study period' covers both the treatment analysis phase and the follow-up analysis phase.

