6.2.2 Other secondary efficacy endpoints

Other secondary efficacy endpoints are defined in Section [3.3.2.2](#).

In general, all endpoints will be summarized using descriptive statistics such as number of observations, means, standard error, and proportions, as appropriate. All analyses will be run on the ITT population.

- Proportion of subjects with at least one treatment-emergent major thromboembolic event (e.g., myocardial infarction, cerebrovascular accident, pulmonary embolism or DVT), confirmed after adjudication, as well as the number of such events, during the overall treatment period (including extensions) (Caplacizumab, Placebo, OL Caplacizumab).
- Proportion of subjects with recurrences of TTP as well as the number of such events during study drug treatment (including extensions) and after study drug treatment (during FU) will be summarized by treatment group (Caplacizumab, Placebo, OL Caplacizumab).
- Proportion of subjects with treatment-emergent clinically significant TTP-related events, as well as the number of such events in the overall study period (including 4-week FU period) as defined in Section [3.3.2.2](#) will be summarized by treatment group (Caplacizumab, Placebo, OL Caplacizumab).
- Area under the curve (AUC) of platelet count until Day 5, truncated at $150 \times 10^9/\text{L}$ if platelet count is $150 \times 10^9/\text{L}$ or above, will be summarized by treatment group (Caplacizumab, Placebo). The AUC value will be calculated using the linear trapezoidal rule, i.e. $AUC_{t_i \text{ to } t_{i+1}} = 1/2 * (C_i + C_{i+1}) * (t_{i+1} - t_i)$ where C_i is the platelet count at time point t_i . Missing platelet counts will not be imputed separately as missing values can be bridged by using the trapezoid rule on neighboring (available) timepoints, thereby implicitly interpolating the missing timepoint. If the subject discontinued prior to Day 5, the subject will not be considered in this analysis. Descriptive statistics will include the 25%, 75% and 90% percentiles.
- Mortality rate (number and percentage) will be summarized by treatment group (Caplacizumab, Placebo, OL Caplacizumab) during DB treatment daily PE period (OL Caplacizumab not applicable), overall treatment period, FU period and overall study period.
- Organ damage markers:
 - Time to LDH $\leq 1 \times \text{ULN}$
 - Time to cTnI $\leq 1 \times \text{ULN}$
 - Time to serum creatinine $\leq 1 \times \text{ULN}$

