- Proportion of subjects who have a platelet count $\geq 150 \times 10^9/L$ on Day 1, 2, 3, 4, 5 and Day 10 and end of study drug treatment (i.e., last weekly visit during the DB or OL treatment period) will be summarized by treatment group (Caplacizumab, Placebo, OL Caplacizumab).
- Proportion of subjects with refractory TTP, defined according to Scully et al. (2016) as lack of sustained platelet count increment or platelet counts $< 50 \times 10^9/L$ and persistently raised LDH ($> 1.5 \times$ ULN) despite 5 plasma exchanges and steroid treatment will be summarized by treatment group (Caplacizumab, Placebo). Refractory TTP is derived as follows: (platelet count at Day x $<$ platelet count at Day x-1 for at least 1 value of x with x=2,...,5) and (LDH $> 1.5 \times$ ULN from Day 1 to Day 5). Subjects who have reached platelet count response (primary endpoint) by Day 5 will be considered as not refractory to TTP. Missing values will be imputed by using multiple imputation (Markov Chain Monte Carlo) by

averaged simulated parameter values, except if the subject discontinued prior to Day 5. In that case, the subject will not be considered in the analysis.

- Time to stop of daily PE: A KM analysis will be conducted with time to stop of daily PE within the DB treatment period as dependent variable and treatment group (Caplacizumab, Placebo) as independent variable. Time to stop of daily PE is defined as: date of daily PE stop - date of first i.v. loading dose of study drug after randomization + 1 day.
- The number of PE days and the total PE volume (absolute and normalized) in the DB treatment daily PE period and the overall treatment period will be summarized by treatment group. For this analysis the treatment groups are defined as
 - Caplacizumab + OL Caplacizumab
 - Placebo + OL Caplacizumab

Subjects will thus be analyzed according to their initial treatment group, both before and after switch to open-label caplacizumab. The number of PE days is defined as the total number of days on which PE is documented. The absolute total PE volume is given by the sum over all PE days of the amount exchanged in liter, while the normalized total PE volume is calculated as the sum over all PE days of the multiple of plasma volume exchanged.

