14.2.6 Safety parameters

Table 14.2.1.6.1: EFF: Safety related parameters – Mortality rate

Number and percentage of subjects who died and mortality rate during each of the 4 time periods: DB treatment daily PE period, overall treatment period, FU period and overall study period.

Population: ITT population.

Table 14.2.1.6.2: EFF: Safety related parameters – Proportion of subjects with evidence of cardiac ischemia and/or arrhythmia/conduction abnormalities

Frequency tabulation of evidence of cardiac ischemia and/or arrhythmia/conduction abnormalities on Days 1, 2, 3, and 4, and Weeks 1 and 5 of 30-day post-daily PE treatment period, and the first and final FU visit.

Population: ITT population.

Table 14.2.1.6.3: EFF: Safety related parameters – Number of days in hospital

Descriptive statistics of the number of days in hospital in 4 time periods: DB treatment daily PE period, overall treatment period, FU period and overall study period.

Population: ITT population.

Table 14.2.1.6.4: EFF: Safety related parameters – Number of days in ICU

Descriptive statistics of the number of days in ICU in 4 time periods: DB treatment daily PE period, overall treatment period, FU period and overall study period.

Population: ITT population.

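### The visible SAP specifies no mortality summary by randomized arm over the overall treatment, follow-up or overall study period

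*SAP*

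**What the plan says.** Mortality is one of the other secondary endpoints. SAP 6.2.2 reports it in three columns ("Mortality rate (number and percentage) will be summarized by treatment group (Caplacizumab, Placebo, OL Caplacizumab") for four periods: double-blind daily PE, overall treatment, follow-up and overall study. The open-label column does not apply to the first of these.

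Three definitions decide where a death is counted:

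- SAP 4.3.6, on the Caplacizumab and Placebo groups: "only data up to the switch are used in the analyses of these treatment groups".
- SAP 4.3.6, on the third group: "The OL Caplacizumab treatment group will only be used for analyses after the switch to open-label caplacizumab".
- SAP 4.3.5: "After switch to open-label caplacizumab an all-treated analysis will be conducted in a separate pooled open-label caplacizumab treatment group, unless specified otherwise".

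A first exacerbation triggers the switch in either arm: "subjects will receive open label caplacizumab together with daily PE irrespective of what the initial treatment allocation was" (protocol synopsis, repeated in 3.1.1 and 3.3). A first relapse during treatment extension does the same. Under SAP 4.4.1 the overall treatment period spans the double-blind and open-label periods, and the overall study period "covers both the treatment analysis phase and the follow-up analysis phase". Both therefore include time after the switch.

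The shell for Table 14.2.1.6.1 (SAP 14.2.6) reads "Number and percentage of subjects who died and mortality rate during each of the 4 time periods". It names the ITT population and does not redefine the groups.

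**The concern.** The switch happens after randomization, and the trial expects it to be affected by treatment, since recurrence is itself a key secondary endpoint. Cutting each arm off at the switch and pooling what follows makes group membership depend on outcome. The last three mortality rows then cannot be read as caplacizumab against placebo as randomized. Death can be counted by randomized arm without any on-treatment rule, and the protocol gives it weight: it cites a background mortality of 10 to 20% (1.1.1) and asks the DSMB to focus on mortality (3.1.1).

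The SAP also treats other endpoints differently. For PE days and volume, 6.2.2 combines periods within the initial arm: "Subjects will thus be analyzed according to their initial treatment group, both before and after switch to open-label caplacizumab". As planned, hospital days over the whole study are by randomized arm and deaths over the whole study are not.

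**Working it through.** The documents state no figure for mortality by arm, so there is none to reproduce. The main check is a reading of the definitions. The arithmetic only gives scale.

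**1. Trace one death.** Take a subject randomized to placebo who has a first exacerbation, starts open-label caplacizumab and then dies.

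- The Placebo column stops at the switch (4.3.6), so the death is not counted there.
- The open-label column takes post-switch data (4.3.6), so the death is counted there.
- A caplacizumab-randomized subject with the same history enters the same column, because it is pooled unless stated otherwise (4.3.5). Neither the mortality text in 6.2.2 nor Table 14.2.1.6.1 states otherwise.
- A death in follow-up after a switch follows the same rule. SAP 4.3.4 likewise pools switchers' follow-up visits.

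**2. Look for another output that restores the arm.**

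- Key secondary endpoint 1 includes TTP-related death but counts only events before a switch (SAP 6.2.1).
- The adverse event tables use the same three groups plus Caplacizumab Total, which takes in the post-switch events of placebo-randomized subjects (SAP 7.1.2).
- The listing of events leading to death (16.2.7.4) and the allocation listing (16.2.1.1) would allow a by-arm count to be rebuilt, but no such summary is specified.

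**3. Compare with the SAP's own alternative.** The groups Caplacizumab + OL Caplacizumab and Placebo + OL Caplacizumab are already defined for corticosteroid use (5.5.1), total treatment duration (5.6), and PE and ICU/hospital days (6.2.2). The protocol lists mortality in four periods without a split at the switch (3.6.4), and SAP 12.1 does not record the split as a change.

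**4. How many subjects could switch?** Inputs: 132 subjects randomized 1:1, so 132 / 2 = 66 per arm (SAP 3.2); Phase II exacerbation during treatment of 28% on placebo and 8% on caplacizumab (protocol 1.2.4). Applying those rates here is an assumption.

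| Assumed rates | Placebo | Caplacizumab | Total | Share of 132 | Placebo share of open-label column |
|---|---|---|---|---|---|
| 28% vs 8% | 0.28 × 66 = 18.5 | 0.08 × 66 = 5.3 | 23.8 | 18% | 18.5 / 23.8 = 78% |
| 30% vs 10% | 0.30 × 66 = 19.8 | 0.10 × 66 = 6.6 | 26.4 | 20% | 19.8 / 26.4 = 75% |

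The second row uses the design rates for the whole composite in key secondary endpoint 1, so it serves as an upper assumption for recurrence alone.

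**5. Effect of one reassigned death.** 1 / 66 = 1.5 percentage points. As a hypothetical, three placebo-arm deaths before a switch give 3 / 66 = 4.5%. One further death after a switch would make the by-arm figure 4 / 66 = 6.1%, and two would make it 5 / 66 = 7.6%. The Placebo column's count would stay at three.

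**The case against.** The strongest defence is that the split is deliberate and consistent. Other clinical events in SAP 6.2.2 (thromboembolism, recurrence, TTP-related events) use the same three columns. Protocol 3.6.4.2 also specifies a descriptive display for key secondary endpoints 1 and 2 in which placebo subjects are assessed only while on placebo. The combined groups are used for cumulative treatment and resource totals, and Placebo + OL mixes two treatments. Deaths after the switch are not hidden: they appear in a labelled column and in listings. Mortality is descriptive and outside the testing hierarchy.

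Most of this stands, and it is why the planned columns should remain. It does not supply the missing summary. The protocol's display is also not the same as the SAP's: it leaves caplacizumab-randomized subjects in one group with no cut-off stated, and its third group holds placebo crossovers only. It gives no precedent for pooling both arms after the switch.

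A reader might infer more than the documents support, in four ways:

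- *That mortality is never tabulated by arm.* SAP 6.4, 7.1.3 and 14.2.8 (exploratory analyses) cannot be read in the public copy, and the disposition table or CONSORT figure may show deaths as a discontinuation reason. The point covers visible, specified summaries only.
- *That those who switch are the sickest.* Recurrence normally requires initial platelet recovery (protocol 3.1.1; SAP 6.2.1 allows an exceptional case). Subjects who die before recovering, or who never recover, ordinarily do not switch and stay in their arm.
- *That 18% of subjects drop out of the randomized columns.* Their pre-switch data stay. The 18% counts possible switchers, not reassigned deaths.
- *That the result is biased in a known direction.* Nothing in the documents establishes one.

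**Conclusion.** The point holds for the visible SAP. In the overall treatment, follow-up and overall study rows, a death after the switch is counted in a column pooled over both arms, and no specified summary returns it to the randomized arm. Those rows are therefore not a randomized comparison. Deaths before a switch, deaths of never-switchers and deaths after a first relapse in follow-up (which triggers no switch) all stay in their arm, and the double-blind daily PE row is a clean by-arm summary.

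Each affected death is worth 1.5 points of an arm's mortality, given 66 per arm. How many there will be is unknown. Phase II reported two deaths, both on placebo between end of study treatment and the one-month follow-up (protocol 1.2.4), without saying whether either subject had crossed over. The figure of about 24 possible switchers rests on Phase II rates carrying over. No hypothesis test or error rate is affected, so this is a cheap improvement to a descriptive table and does not threaten the confirmatory results.

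**What to change.** In Table 14.2.1.6.1, keep the planned columns and add Caplacizumab + OL Caplacizumab and Placebo + OL Caplacizumab for the overall treatment, follow-up and overall study rows. Use all ITT subjects in the arm as denominator for the overall treatment and overall study rows, and state the denominator used for the follow-up row. Give the between-arm difference with a 95% CI, as description only. Add a footnote that Placebo + OL includes time on open-label caplacizumab. Carry the same group definition into the mortality bullet of SAP 6.2.2.

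The cost is two columns and a footnote, using groups the SAP already defines and data already collected. The drawback is that the combined placebo arm includes post-crossover exposure to caplacizumab, which is why the planned columns should stay beside it.

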In another, prospective cohort study of 133 TTP patients with severe ADAMTS13 deficiency (ADAMTS13 activity < 10%) for whom frozen samples on diagnosis were available for cardiac TnI (cTnI) measurement, 78 patients (59%) had cTnI > 0.1 µg/mL. Thirty-three patients (25%) in this cohort died and 19 patients (17%) were assessed with refractory disease (absence of platelet count doubling after 4 days of standard of care treatment with persistently high LDH levels). A cut off value for cTnI predicting death was determined as 0.25 µg/mL. Patients with cTnI at baseline > 0.25 µg/mL showed more cerebral and cardiac involvement and experienced a more severe outcome with a higher death rate: 3-fold increase in risk of death or refractory disease [7]. These results suggest that more rapidly reducing further microvascular cardiac ischemia, e.g. measured by troponin, of the presenting TTP episode could be expected to have a clinical benefit. Other retrospective reports found similar results on acute and long-term cardiac involvement in TTP patients including myocardial infarctions [8] and other cardiac events like infarctions, arrhythmias, cardiogenic shock and sudden cardiac death [9].

In addition to the cardiac manifestations, neurological involvement is considered to be one of the differentiating factors for TTP. It is observed in more than half of patients presenting

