4.3 Key Definitions and Labels

4.3.1 Definition of baseline

Baseline is defined as the last non-missing assessment before first administration of study drug.

For assessments with multiple parameters per subject (such as laboratory assessments), baseline will be determined per parameter individually. It is recognized that baseline assessments may thus come from more than one assessment and not just from the “baseline visit” assessment. Baseline will be calculated for each treatment period separately (double-blind treatment and open-label treatment). The assessment on Day 1 of the open-label treatment period, taken before first administration of open-label caplacizumab, will be taken as baseline value for the open-label part.

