A separate KM analysis for each organ damage marker will be conducted with time to first normalization as dependent variable and treatment group (Caplacizumab, Placebo) as independent variable. Subjects in either initial treatment arm who have switched to open-label caplacizumab before having reached the endpoint will be censored at time of switch.

Time to first normalization of *organ damage marker* is defined as: first time of *organ damage marker* \leq ULN - time of first i.v. loading dose of study drug after randomization + 1 minute. All on-treatment records during DB treatment period will be used. The time to first normalization will be represented by number of days with two decimal digits.

- Proportion of subjects with increases in organ damage markers (cTnI and serum creatinine) above $1 \times$ ULN will be summarized by treatment group (Caplacizumab, Placebo, OL Caplacizumab) during DB treatment daily PE period (OL Caplacizumab not applicable), overall treatment period, FU period and overall study period.
- AUC of cTnI above $1 \times$ ULN (cTnI peak) will be summarized by treatment group (Caplacizumab, Placebo, OL Caplacizumab) during DB treatment daily PE period (OL Caplacizumab not applicable) and during overall treatment period. The AUC value will be calculated by the linear trapezoidal rule. The analysis will be repeated including and excluding cTnI peaks at baseline. Descriptive statistics will include the 25%, 75% and 90% percentiles.
- Proportion of subjects with neurological symptoms based on neurological assessment on Day 1, 2, 3, 4, 5 and Weeks 1 and 5 of 30-day post-daily PE treatment period, and the first and final FU visit will be summarized by treatment group (Caplacizumab, Placebo, OL Caplacizumab).
- Actual value and change from baseline in Standardized mini mental state examination (SMMSE) total score on Days 1, 2, 3, 4, 5 and Weeks 1 and 5 of the 30-day post-daily PE treatment period, and the first and final FU visit will be summarized by treatment group (Caplacizumab, Placebo, OL Caplacizumab). For the OL Caplacizumab treatment group change from baseline is based on the Day 1 assessment of the open-label treatment period.
- Proportion of subjects with evidence of cardiac ischemia and/or arrhythmia/conduction abnormalities on Days 1, 2, 3, and 4, and Weeks 1 and 5 of 30-day post-daily PE treatment period, and the first and final FU visit will be summarized by treatment group (Caplacizumab, Placebo, OL Caplacizumab).

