14.2.3 Organ damage markers

Table 14.2.1.3.1: EFF: Organ damage marker levels – Key secondary endpoint: Time to normalization of all 3 of the organ damage marker levels

Kaplan-Meier analysis stratified for GCS at randomization and LDH status (\leq ULN / $>$ ULN) at baseline, including a two-sided stratified Log-rank test. The output will include number of events, number of censored values, median, 25% and 75% time to event with 95% CIs and p-value of the log-rank test. If the model does not allow parameter estimation due to limited observations in subcategory combinations, GCS stratification factor will be omitted from the analysis.

Population: ITT population.

Table 14.2.1.3.2: EFF: Organ damage marker levels – Time to normalization of LDH

Kaplan-Meier analysis. The output will include number of events, number of censored values, median, 25% and 75% time to event with 95% CIs.

Population: ITT population.

Table 14.2.1.3.3: EFF: Organ damage marker levels – Time to normalization of cTnI

Kaplan-Meier analysis. The output will include number of events, number of censored values, median, 25% and 75% time to event with 95% CIs.

Population: ITT population.

Table 14.2.1.3.4: EFF: Organ damage marker levels – Time to normalization of serum creatinine

Kaplan-Meier analysis. The output will include number of events, number of censored values, median, 25% and 75% time to event with 95% CIs.

Population: ITT population.

Table 14.2.1.3.5: EFF: Organ damage marker levels – Proportion of subjects with increases in organ damage markers

Frequency tabulation of increased organ damage markers ($>$ ULN), by marker (cTnI and serum creatinine) and analysis period (DB treatment daily PE period, overall treatment period, FU period and overall study period).

Population: ITT population.

Table 14.2.1.3.6: EFF: Organ damage marker levels – AUC of cTnI $>$ ULN

Descriptive statistics of AUC(cTnI) $>$ ULN during DB treatment daily PE period and during overall treatment period. Separate tabulation including and excluding cTnI peaks at baseline.

Population: ITT population.

Table 14.2.1.3.7: EFF: Organ damage marker levels – Actual values at each time point

Descriptive statistics of LDH, cTnI and serum creatinine at each time point.

Population: ITT population.

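### The organ damage marker endpoint is named as an increase above 1 x ULN but tabulated as >ULN with no baseline condition, so persisting baseline elevation is mixed with new rises

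*SAP*

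**What the plan says.** SAP 3.3.2.2 and 6.2.2 (and Protocol 3.6.4) name the endpoint as "Proportion of subjects with increases in organ damage markers (cTnI and serum creatinine) above" 1 x ULN. The SAP reports it for the double-blind (DB) daily PE period, the overall treatment period, the follow-up (FU) period and the overall study period. Neither SAP section says how an increase is derived.

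The derivation has to be read from the table index in SAP 14.2.3. Table 14.2.1.3.5 is described as "Frequency tabulation of increased organ damage markers ($>$ ULN), by marker (cTnI and serum creatinine) and analysis period". The population is ITT; SAP 6.2.2 says of these endpoints generally that "All analyses will be run on the ITT population".

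Three other provisions bear on the reading:

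- SAP 4.3.1: "Baseline is defined as the last non-missing assessment before first administration of study drug".
- SAP 4.4.1, Table 1: the DB daily PE period begins at "First administration datetime of DB treatment".
- SAP 6.2.2, in the next bullet, on the AUC of cTnI above ULN: "The analysis will be repeated including and excluding cTnI peaks at baseline".

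SAP 5.3 already derives a baseline category of ≤ULN or >ULN for each marker. Nothing links that category to this endpoint.

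**The concern.** The word increase suggests a change from a lower state to a higher one. The table rule describes a state: above ULN at some point in the period. In this trial the two can differ, because some subjects will enter with raised cTnI or creatinine. The SAP expects this, since it tabulates baseline status and makes time to normalization an endpoint.

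A reader of the finished table would probably take the proportion as the frequency of new cardiac or renal injury on treatment. Part of it would instead be elevation present before the first dose that had not yet cleared. An effect on new rises would look small in relative terms. A difference between arms could also come from unequal baseline status, or from faster normalization, which the time-to-normalization endpoints already measure.

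**Working it through.** The documents state no sample size, power or expected value for this endpoint, so there is no figure to reproduce. The check has a textual part and an arithmetic part.

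**Text.** Take a subject whose cTnI is above ULN before the first dose, lower but still above ULN on Day 2, and normal from Day 4.

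1. Day 1 assessments precede the i.v. dose (footnote a to the daily PE schedule). That value is the baseline and lies outside the DB period.
2. Organ damage markers are sampled daily in the daily PE period, so the Day 2 value lies inside it and is >ULN.
3. Under the Table 14.2.1.3.5 rule the subject is counted in the DB daily PE, overall treatment and overall study periods, although the marker only fell.
4. A subject who was elevated at baseline but normal at every in-period sample is not counted. The table is therefore not simply baseline prevalence.

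**Arithmetic.** Let p be the share >ULN at baseline, r the share of those with at least one in-period value >ULN, and q the share of baseline-normal subjects who newly rise. Then:

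tabulated proportion = p·r + (1 − p)·q

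All three inputs are assumptions. For illustration p = 0.59, taken from a cohort cited in Protocol 1.1 ("78 patients (59%) had cTnI" above that study's cut-off; 78/133 = 58.6%), and r = 0.9.

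*Equal persistence, new rises 15% vs 5% among baseline-normal subjects:*

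- Placebo: 0.59 × 0.9 + 0.41 × 0.15 = 0.531 + 0.0615 = 59.3%
- Caplacizumab: 0.59 × 0.9 + 0.41 × 0.05 = 0.531 + 0.0205 = 55.2%
- Difference 4.1 points; ratio 0.5515/0.5925 = 0.93

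New rises alone on the same all-subject denominator are 6.15% vs 2.05%: difference 4.1 points, ratio 0.33. The absolute difference is unchanged and the ratio moves from 0.33 to 0.93. Over p = 0.3 to 0.8 and r = 0.5 to 1.0 the tabulated ratio runs from 0.73 to 0.98. The difference equals (1 − p) × 0.10 throughout, that is 7.0 down to 2.0 points.

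*Different persistence, no effect on new rises (q = 0.10 in both arms, r = 0.9 vs 0.8):*

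- 0.59 × 0.9 + 0.41 × 0.10 = 57.2%
- 0.59 × 0.8 + 0.41 × 0.10 = 51.3%
- Difference 5.9 points, all from speed of normalization

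*Chance imbalance.* Randomization is stratified by GCS only. With 132/2 = 66 per arm and p = 0.59, the standard deviation of the between-arm difference in baseline elevation is √(2 × 0.59 × 0.41/66) = 8.56 points. An imbalance d moves the tabulated difference by d × (r − q). At r = 0.9, one standard deviation moves it by 8.56 × 0.75 = 6.4 points (q = 0.15) to 8.56 × 0.85 = 7.3 points (q = 0.05).

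**The case against.** The strongest reply is that this is an unfinished derivation in a table index, not a decision to count improving subjects. The endpoint text says increases; the SAP nowhere says any value, and nowhere says that the endpoint is meant to isolate new injury. That is fair as to intent. But >ULN by marker and period is the only rule a programmer is given, and SAP 4.3.3 admits unscheduled values when a worst case over a period is derived. The rule needs correcting or clarifying whichever was intended.

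Other planned outputs also cover part of the ground, and this stands:

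- Tables 14.3.2.5 and 14.3.2.7 cross-tabulate creatinine categories, split at 1 x ULN, against baseline in the safety population. They work by time point and by worst post-baseline value, not by the four periods, but they show baseline-normal subjects who rise. cTnI is not among their parameters.
- Baseline status is tabulated by arm, so an imbalance would be visible.
- Time to normalization addresses persistence, and the cTnI AUC is repeated without baseline peaks.

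A reader might infer that the table shrinks a true 10-point benefit to 4.1 points. The documents do not support that. Ten points among baseline-normal subjects and 4.1 points among all randomized subjects are the same effect on two denominators (0.41 × 0.10).

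A reader might also infer that about 59% of this trial's subjects will have raised cTnI at baseline. That figure uses a fixed cut-off, not this trial's ULN, and samples taken at diagnosis from patients with severe ADAMTS13 deficiency. Baseline here follows one PE, with no ADAMTS13 threshold for entry. Protocol 3.1.2 notes that not every patient has each marker raised, and no baseline prevalence is given for creatinine.

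**Conclusion.** The point holds. Followed as written, Table 14.2.1.3.5 counts persisting baseline elevation and new rises together under the name of increases. This dilutes the ratio between arms and leaves the contrast open to baseline imbalance and to differing speed of normalization. It does not attenuate the absolute difference on the ITT denominator when persistence is equal between arms.

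No expected size can be given, because the share elevated at baseline, their persistence and the new-rise rate are all unknown for this trial; the figures above show direction only. The conclusion rests on reading a per-subject, per-period >ULN frequency as at least one value >ULN in the period, which is the natural reading but not the SAP's wording.

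The consequence is limited. The endpoint is descriptive and outside the testing hierarchy, so no confirmatory conclusion depends on it. What no planned table supplies is mainly a new-rise proportion for cTnI.

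**What to change.** In SAP 6.2.2 and Table 14.2.1.3.5:

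- Present the table by baseline status, ≤ULN or >ULN. Use the DB baseline for the Caplacizumab and Placebo columns, the open-label (OL) baseline for the OL Caplacizumab column, and the last value before follow-up for the FU period.
- Count an increase as a later value >ULN among subjects who were ≤ULN at that baseline.
- Keep the present all-subject row, relabelled as any value >ULN.

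I would not add a rule that counts baseline-elevated subjects whenever a later value exceeds their own baseline. With daily sampling it would pick up trivial fluctuation.

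The DB baseline categories are already planned in SAP 5.3 and no new data are needed. The cost is a short text change, the corresponding status for the OL and FU periods, a few extra table rows, and a smaller denominator in the baseline-normal row.
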